Subjects will undergo a second surgery at UPMC Presbyterian Hospital approximately 1 year after implantation of the NeuroPort Arrays. It is possible that the NeuroPort Arrays may be explanted earlier due to technical problems, clinical complications, investigator-initiated withdrawal, or subject-initiated withdrawal. The participant will go through standard pre-operative screening procedures which may include a blood draw. The subject will be fully anesthetized throughout the surgery and will receive antibiotics intravenously as with the implantation surgery. The hair will be clipped in the area of the planned surgery. A skin incision will be made from the Patient Pedestal to the area of the craniotomy. It is possible that fibrous tissue will have formed around the wire bundles and NeuroPort Arrays and this will be dissected away prior to explantation. Impedance testing may also be conducted during surgery. Impedance testing measures voltages when very small currents are driven to the electrodes for a short period of time. It is an approved function of the array and no additional risks are expected. The bone flap will be dissected from the dura and lifted and the dura will be opened. The NeuroPort Arrays will most likely be encased in a membrane that appears to be continuous with the arachnoid. The membrane will be cut open and the NeuroPort Arrays will be removed with forceps. The bone flap will be repositioned and secured with titanium or absorbable miniplates. The skin will be repositioned and closed with skin sutures or staples. The entire surgical procedure is expected to take approximately 3 hours.

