2.5 Study outcome evaluations

2.5.1 Study endpoints

The NeuroPort Arrays will be removed 1 year (+/- 30 days) after implantation. A participant will be considered a success for safety if the device is not explanted for safety reasons during the 12-month post-implant evaluation. If the subject experiences treatment resistant (serious) adverse events, he or she will be withdrawn and the arrays will be explanted early (See Section E 2.4.4). The study may also end early if the subject is non-compliant (See Section E 2.4.4).

We believe it is possible that a participant will not want the array removed. If the participant wants the NeuroPort Arrays to stay in, the study PI and neurosurgeon will assess whether this is acceptable. This decision will be based on whether or not the participant is at increased risk by leaving the arrays in and whether the device is still measuring neural activity that is sufficient for brain control. We will consult our DSMB if conflicts arise. One participant in the BrainGate trial has had a NeuroPort Array implanted for more than 1000 days without adverse event [9]. If the NeuroPort Arrays remain implanted for more than 1 year, we will continue to perform clinical follow-up as described in the current protocol. We may also continue brain-machine interface testing although the frequency of the training sessions may be reduced. We will remove the NeuroPort Arrays at anytime as directed by the participant, or as dictated by their clinical condition.

If the participant wishes to leave the NeuroPort Array implanted, but the study PI and neurosurgeon do not feel that it is in their best interest, the participant will be counseled that they should have the NeuroPort Array removed and that not doing so could result in clinically significant adverse events. They will also be informed that brain-machine interface training will not continue. The consent form includes a statement that participants will be financially liable for any medical care resulting from complications of not having the device removed upon instruction of the study PI. We will however allow participants to have the device removed at anytime and the explantation costs would be covered by this study.

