Specific Aim 3: Source localization (combining the MEG and structural MRI data) will be used to identify the anatomical foci of cortical activation controlling imagined and/or attempted movement. The coordinates (x,y,z) of the center of activation can be computed with fMRI or MEG relative to the head coordinate system defined using bony landmarks. The location and area of cortical activation measured by fMRI and MEG during imagined and/or attempted movement will be compared for each subject. A paired t-test will be used to compare location and area of cortical activation measured by the two imaging techniques using data from all participants, although the power of this test may be limited by sample size. Qualitative comparisons will be informative and we expect agreement between the two imaging techniques in terms of localizing the area for array implantation. MEG

potentially offers additional information due to higher temporal resolution.

Specific Aim 3a: Cortical modulation will be calculated as the power of the 4-40 Hz frequency band of MEG data that is recorded during imagined and/or attempted movement. Specific Aim 3a will be evaluated by applying repeated measures ANOVA to test for differences in modulation (magnitude and total area) during imagined and/or attempted movement during the pre-surgical procedures and the follow-up sessions.

The study will be considered a success if the device is not explanted for safety reasons during the 12-month post-implant evaluation. Further participants should demonstrate successful control of a high degree of freedom assistive technology in order to safely perform a task that replicates normal activities of daily living, such as grasping a cup with a robotic manipulator. This study is not being proposed to support marketing applications (510(k) or PMA) for the NeuroPort Arrays. Instead, the goal is to demonstrate that three-dimensional microelectrode arrays provide a safe way to record sufficient neural information for controlling complex assistive devices that will increase the independence of individuals with disabilities.

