3.5 Study outcome evaluations

3.5.1 Study endpoints

The NeuroPort Arrays will be removed up to 5 years after implantation. A participant will be considered a success for safety if the device is not explanted for safety reasons during the 5 year post-implant evaluation. If the subject experiences treatment resistant (serious) adverse events, he or she will be withdrawn and the arrays will be explanted early (See Section E 3.4.4). The study may also end early if the subject is non-compliant (See Section E 3.4.4).

If the participant wishes to leave the NeuroPort Array implanted after 5 years, the participant will be counseled that they should have the NeuroPort Array removed and that not doing so could result in clinically significant adverse events. They will also be informed that brain-machine interface training will not continue. The consent form includes a statement that participants will be financially liable for any medical care resulting from complications of not having the device removed upon instruction of the study PI. We will however allow participants to have the device removed at anytime and the explantation costs would be covered by this study.

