Specific Aim 3: Source localization (combining the MEG and structural MRI data) will be used to identify the anatomical foci of cortical activation controlling imagined and/or attempted movement. The coordinates (x,y,z) of the center of activation can be computed with fMRI or MEG relative to the head coordinate system defined using bony landmarks. The location and area of cortical activation measured by fMRI and MEG during imagined and/or attempted movement will be compared for each subject. A paired t-test will be used to compare location and area of cortical activation measured by the two imaging techniques using data from all participants, although the power of this test may be limited by sample size. Qualitative comparisons will be informative and we expect agreement between the two imaging techniques in terms of localizing the area for array implantation. MEG potentially offers additional information due to higher temporal resolution.

Specific Aim 3a: Cortical modulation will be calculated as the power of the 4-40 Hz frequency band of MEG data that is recorded during imagined and/or attempted movement. Specific Aim 3a will be evaluated by applying repeated measures ANOVA to test for differences in modulation (magnitude and total area) during imagined and/or attempted movement during the pre-surgical procedures and the follow-up sessions.

Specific Aim 4: Sleep quality measures will be correlated to BMI performance on the following day while controlling for differences in task difficulty. Linear regression will be used to determine the most predictive sleep quality metrics.

The study will be considered a success if the device is not explanted for safety reasons during the 12-month to 5 year post-implant evaluation. This study is not being proposed to support marketing applications (510(k) or PMA) for the NeuroPort Arrays. Instead, the goal is to demonstrate that three-dimensional microelectrode arrays provide a safe way to record sufficient neural information for controlling complex assistive devices that will increase the independence of individuals with disabilities.

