In general, the surgical risks associated with implanting the NeuroPort Arrays are anticipated to be typical for any surgery for implanting a device in the brain. The risks should be similar to those for implanting a Deep Brain Stimulator (DBS). However, unlike a DBS implant, the NeuroPort Arrays are not implanted deep into the brain, but rather on the surface of the cortex. The risks associated with surgery include adverse reactions to surgical procedure, bleeding during surgery, infection post-surgery and potential tissue damage to the primary motor cortex during implantation of the NeuroPort Arrays. The risks associated with explantation surgery of the NeuroPort Array are similar to those during implantation surgery. Animal study data show that post-explantation, the primary motor cortex heals with no external signs of irreversible adverse effects. There is also a risk of developing a pressure sore during surgery for individuals with SCI.

There is a risk of bone resorption after the two surgeries where the bone flap is removed and replaced. The bone flap may breakdown and not heal properly however this risk is rare (<1%). If this occurs, the study neurosurgeon may perform an additional surgical procedure to replace the bone flap with an artificial material.

The subject will be under general anesthesia for the duration of the surgery. Minor risks of general anesthesia include nausea and vomiting (25%), sore throat (10-50%), post-operative pain (10-30%), headache (20%), drowsiness (50%), dizziness (20%), damage to the teeth or oral tissue (<1%), and peripheral nerve injuries (<0.3%). These risks are common but are typically temporary. Serious risks of general anesthesia, which are very rare (40), include: vision loss or blurriness (0.0008%), hearing loss (0.01%), anaphylaxis (allergic reaction, 0.01%), post-operative cognitive dysfunction (difficulty with concentration and memory, 1% for individuals over the age of 60), respiratory complications (0.03%), cerebrovascular accident (stroke, 1%), and cardiac arrest (<0.01%).

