There is a risk that it may not be possible to remove one or both of the arrays due to fibrosis (excessive tissue growth). We believe that it is very unlikely (<1%) that this will occur. If the risk of damage to the cortex outweighs the priority to remove the Arrays, our surgeon sub-investigator would cut the lead wire and remove the pedestal(s) leaving the 4 x 4 mm array(s) implanted. The risk of migration would be minimal since the array would be encased in the fibrous tissue. It is possible that the participant may not be able to have an MRI if the array(s) remains implanted since MR safety guidelines differ between institutions. The procedure for evaluation would be similar to other devices that remain implanted near the brain such as titanium plates, metal (aneurysm) clips, and silastic catheters. We do not expect that additional follow-up, beyond the 2 planned visits (1 and 4 weeks post explant) with the neurosurgical team, will be required. We do not believe that extending the implantation duration for up to 5 years increases the risk of fibrosis that would make it more difficult to remove the array.

Steps taken to minimize these risks:

The neurosurgeon sub-investigator will evaluate the extent of fibrosis prior to removing the arrays and determine whether they can be removed safely. The neurosurgeon sub-investigator is board-certified and experienced in removal of implanted devices. Based on our experience with non-human primate research at the University of Pittsburgh and the published results of the human BrainGate trials, we believe that the risk of having to leave the arrays implanted is very low (<1%).

Risks of Post-Operative Head CT (Computed Tomography) (Core Study)

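### Safety success depends only on why an array is removed, so serious harm from the planned explant surgery, or an array that cannot be removed, still scores as a success

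*Combined protocol and SAP*

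**What the plan says.** The safety rule appears four times in the combined protocol and SAP, each time with one component.

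- Core study, per participant (2.5.1): "A participant will be considered a success for safety if the device is not explanted for safety reasons during the 12-month post-implant evaluation".
- Core study, overall (2.5.3): "The study will be considered a success if the device is not explanted for safety reasons during the 12-month post-implant evaluation". That section adds a device-control requirement but nothing further on safety.
- Extension, per participant (3.5.1): "A participant will be considered a success for safety if the device is not explanted for safety reasons during the 5 year post-implant evaluation".
- Extension, overall (3.5.3): the device is "not explanted for safety reasons during the 12-month to 5 year post-implant evaluation".

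Explantation is a scheduled part of the intervention. Section 2.5.1 says "The NeuroPort Arrays will be removed 1 year (+/- 30 days) after implantation", and section 2.4.2 says "Subjects will undergo a second surgery at UPMC Presbyterian Hospital approximately 1 year after implantation of the NeuroPort Arrays". Section 3.4.2 places it at about 5 years for the extension. It is done under general anesthesia, the bone flap is lifted again and the dura is reopened (2.4.2). Section 4.1, under the surgical risks, states: "The risks associated with explantation surgery of the NeuroPort Array are similar to those during implantation surgery". The fibrosis part of 4.1 adds: "There is a risk that it may not be possible to remove one or both of the arrays due to fibrosis". In that case the lead would be cut and the array left in place, a risk put at under 1%.

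**The concern.** The stated goal in 2.5.3 and 3.5.3 is to show that the arrays are a safe way to record. For a device that is meant to come out, removal is part of that question. The success rule looks only at whether safety was the reason for explanting. It does not ask what happened to the participant at surgery or whether the array came out.

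This matters most in the extension. Section 4.1 records a belief that up to 5 years of implantation does not raise the risk of fibrosis that hinders removal. The extension is where that belief can be checked, and the check takes place at explantation. The extension's success rule cannot register the result, whichever way it falls.

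**Working it through.** The plan gives no target safety rate, threshold or power for this endpoint, so there is no figure to reproduce. The check applies the stated rule to the outcomes that the plan itself foresees.

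**Scoring under the rule as written**

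| Course | Explanted for safety reasons in the window? | Score |
|---|---|---|
| Early removal for an infection that resists treatment | Yes | Failure |
| Serious effect of implant surgery, device stays in | No | Success |
| Scheduled explant, serious complication of that operation | No | Success |
| Scheduled explant, array cannot be removed | No | Success |
| Scheduled explant, uneventful | No | Success |

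The last four rows cannot be told apart. A retained array even meets the words of the rule, since it was not explanted.

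**Is the cause the window or the event?** Taking 12 months as day 365, planned removal falls between day 365 - 30 = 335 and day 365 + 30 = 395 (2.5.1). The second post-explant visit is at 4 weeks +/- 3 days (2.4.3), that is 25 to 31 days later, or day 335 + 25 = 360 to day 395 + 31 = 426. Explant, and on the earliest schedule even the last clinical visit, can fall inside 12 months. The score is still a success, because harm from the operation is not the counted event. The cause is therefore mainly the event definition.

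**Size**

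- Inputs: at most 5 implanted (2.5.2); risk of having to leave an array in place below 1% (4.1, fibrosis).
- Assumptions: all 5 come to explantation, the rate applies per participant, and outcomes are independent.
- Formula: P(at least one) = 1 - (1 - p)^5.
- At p = 0.01: 1 - 0.99^5 = 1 - 0.951 = 0.049. Since p is below 1%, the chance is below 4.9%.
- If one such case occurs, it is 1/5 = 20% of the safety result.

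Section 4.1 gives rates for some single surgical and anesthetic events but no overall rate for serious complications of explantation, so no total is computed.

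**The case against.** The strongest reply is that safety does not rest on this label. Aim 1a is met by documenting adverse events throughout the trial (2.5.3, 3.5.3). Table 1 marks adverse event assessment through explant and end of study. Clinical visits follow at 1 and 4 weeks (2.4.3, 3.4.3), device-associated effects are followed until they resolve or stabilize (4.2.3), and wound events go to the DSMB chair within 24 hours (4.2.5). With at most 5 implants, single-subject analysis and no marketing purpose, every explant event would be seen individually. Sections 2.5.1 and 3.5.1 also send serious events that resist treatment to early explant, which does count as failure. All of this stands. It answers any worry about lost data, but it does not change a success rule that the plan states four times.

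A reader might infer more than the documents support, in four ways:

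- **That explant harm goes unrecorded.** It does not, as shown above.
- **That the problem is a window closing before explantation.** Scheduled removal can fall inside 12 months, and implant-surgery harm well inside the window is not counted either.
- **That the 5-6% to under 9% infection estimate in 4.1 can serve as the explant complication rate.** It is given for chronic implantation with percutaneous pedestals, which explantation removes. Nothing in the plan supports carrying it over.
- **That 5 years of implantation makes removal harder.** Section 4.1 states the opposite belief. The point here is only that the success rule cannot test it.

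**Conclusion.** The point holds as a defect in the success criterion. In all four places a participant can have a serious effect of implant or explant surgery, or be left with an array that could not be removed, and still be scored a safety success. This follows from the wording and depends on no assumed rate.

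The only size that the plan's own figures support is a chance below 4.9% of at least one non-removable array among 5 participants, under the assumptions listed. The frequency of other serious explant complications is unknown from the documents. Because the data are already collected and no test or go/no-go decision uses the label, this is an inexpensive improvement to the safety conclusion. It is not a threat to the study.

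**What to change.** Keep the existing 12-month and 5-year criterion. In 2.5.1, 2.5.3, 3.5.1 and 3.5.3 add a second safety component, scored per participant:

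1. Any serious adverse effect associated with the device, or with implant or explant surgery, from implantation through the planned 4-week post-explant visit.
2. Whether each array was removed, with the extent of fibrosis that the neurosurgeon already evaluates at surgery (4.1).

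State the safety conclusion on both components, and specify:

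- **Where it is scored.** The explant part belongs to whichever study, core or extension, the explant occurs in. Simply running the core endpoint to the post-explant visit would not work: participants may enter the extension for up to 4 more years (3.3.3) or keep their arrays (2.5.1, 3.5.1), so some could not be scored for years, or ever.
- **Missing outcomes.** Post-explant visits are scheduled at discretion (2.4.3, 3.4.3) and are only encouraged after withdrawal (2.4.4, 3.4.4). Report participants who keep their arrays or miss these visits as not yet evaluable for the explant part, not as successes, unless a qualifying event is already on record.
- **Follow-up length.** The chronic-recording part of 4.1 gives at least three weeks after explant, while 2.4.3, 3.4.3 and the fibrosis part of 4.1 give visits at 1 and 4 weeks. These passages must be reconciled, because the component ends there.

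The change affects scoring and reporting only. It needs no new visit or measurement and no change to clinical care. The cost is that the safety result may look less favourable, and that the explant part arrives about a month after explantation, which for extension participants may be years after the 12-month result.

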2.5.2 Sample size determination

A maximum of 10 participants will be enrolled in order to implant a maximum of 5

subjects. Because it is possible that a subject may enroll and then be determined to be ineligible for anesthesia and/or surgery, the maximum number of subjects enrolled may exceed the number implanted.

New information will be learned with each participant, as this is a feasibility study. Single-subject design statistical analyses will be used. Our main goal is to demonstrate the safety and efficacy of NeuroPort Arrays for long-term recording of neural activity in order to control a high-dimensional BMI.

2.5.3 Outcome data and data analysis

Specific Aim 1a will be fulfilled through monthly clinical examinations as well as observations made by the research staff, participant, or their caregiver throughout the trial. Research staff will document volunteered and observed adverse events at least weekly during the BMI training sessions. Adverse events will be documented and reported to University of Pittsburgh IRB and to the FDA in accordance with the respective reporting requirements and in the annual report. This documentation will serve as documentation of the safety of device in this small sample.

Specific Aim 1b is to characterize signal quality (firing rate, number of units recorded) over the duration of implantation. Data to support this aim will be collected at least weekly during the BMI training sessions. Our primary method of analysis will be to plot the trends in signal quality measures over time. The trend will be quantified using regression techniques.

Specific Aim 2 is to demonstrate that individuals with tetraplegia can learn to successfully control of a variety of external devices and computer-driven tasks using signals recorded with the NeuroPort Array. In addition to video documentation of brain-controlled device operation, we will quantify the number of degrees of freedom achieved by each participant at regular intervals for the duration of implantation. Multiple baselines will be defined as the level of computer assist will decrease with training. We will use regression to quantify changes in performance at a given assist level. Similarly, trends in success rate and computer assist level for a given task will be quantified over the duration of the trial using regression.

Specific Aim 3: Source localization (combining the MEG and structural MRI data) will be used to identify the anatomical foci of cortical activation controlling imagined and/or attempted movement. The coordinates (x,y,z) of the center of activation can be computed with fMRI or MEG relative to the head coordinate system defined using bony landmarks. The location and area of cortical activation measured by fMRI and MEG during imagined and/or attempted movement will be compared for each subject. A paired t-test will be used to compare location and area of cortical activation measured by the two imaging techniques using data from all participants, although the power of this test may be limited by sample size. Qualitative comparisons will be informative and we expect agreement between the two imaging techniques in terms of localizing the area for array implantation. MEG

potentially offers additional information due to higher temporal resolution.

Specific Aim 3a: Cortical modulation will be calculated as the power of the 4-40 Hz frequency band of MEG data that is recorded during imagined and/or attempted movement. Specific Aim 3a will be evaluated by applying repeated measures ANOVA to test for differences in modulation (magnitude and total area) during imagined and/or attempted movement during the pre-surgical procedures and the follow-up sessions.

The study will be considered a success if the device is not explanted for safety reasons during the 12-month post-implant evaluation. Further participants should demonstrate successful control of a high degree of freedom assistive technology in order to safely perform a task that replicates normal activities of daily living, such as grasping a cup with a robotic manipulator. This study is not being proposed to support marketing applications (510(k) or PMA) for the NeuroPort Arrays. Instead, the goal is to demonstrate that three-dimensional microelectrode arrays provide a safe way to record sufficient neural information for controlling complex assistive devices that will increase the independence of individuals with disabilities.

